- Potential for progressive SCI including neurodegenerative SCI, ALS, cancer myelopathy, Multiple sclerosis, transverse myelitis
- History of central nervous system disorder (i.e. prior SCI, stroke, brain injury, Parkinson's disease, MS, etc.)
- History of peripheral neuropathy
- pre-SCI symptoms of peripheral neuropathy (numbness and/or tingling in feet, sharp/jabbing/burning pain in feet, sensitivity to touch, lack of coordination, muscle weakness, etc.)
- Pregnancy
- Known injury to the lumbosacral spinal cord or plexus, or pelvis with associated neuropathy
- concern for tibial nerve pathway injury
- absence of toe flexion or autonomic dysreflexia during electric stimulation test
- bladder chemodenervation in prior 6 months

5. Withdrawal Criteria

Possible reasons for discontinuation of study intervention:

- Intolerable incontinence after discontinuation of bladder medications
- Intolerant to electric stimulation
- Non-compliance

To mitigate non-compliance, a stipend for effort in completing voiding diary will be provided at \$10 per day (2 days per month). An additional \$20 will be provided for logging bladder medication use and TTNS use/settings monthly. If both voiding diary and TTNS diary are reported, a \$10 bonus will be provided, therefore \$70 month 1, and \$50 for each months 2 and 3. At most per subject= \$170 for the 3-month trial per subject. Subjects will also receive reimbursement for travel for the urodynamic studies up to \$200 per trip (two urodynamic studies = up to \$400 per subject) and if medication reduction requires new prescriptions to cover co-payments when applicable up to \$50 total per subject.

6. Subject Replacement

Subjects who drop out will be replaced by recruitment from the SCI clinic and asking for informed consent from those who meet the I/E criteria.

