Medication reduction protocol: Subjects will be using up to 2 anticholinergic OAB medications. Subjects generally use similar medications with a common approach- maximize one medication before adding a second medication. The PI will provide a weekly weaning schedule, individualized for each subject. No changes will occur during the first 2 weeks of TTNS. Starting week 3, the secondary OAB medication will be halved if possible, otherwise discontinued. Should the subject tolerate this, weaning will continue until one medication is discontinued, then the other. If the subject does not tolerate weaning, they will remain on the lowest, tolerable dose and we will attempt weaning the following week.

- Information gathered:
 - Clinical demographics, morbidity, and Neurologic Exam findings from interview with subjects, exam, and EMR review.
 - Bladder diary will include:
 - use of TTNS with amperage and presence of toe flexion, and pain score 0-10
 - log of catheterization, volumes
 - log of incontinence episodes
 - Description of other observed changes, including but not limited to: fatigue, vision changes, mental status, bowel program changes, and sexual function changes.
 - I-QOL at baseline initial visit and then at 3-month follow-up. Can be conducted over phone.

- NBSS at baseline and every 4 weeks (monthly) and at the 3-month follow-up. Can be conducted over phone.
- Anticholinergic survey at baseline and then at 3-month follow-up. Can be conducted over phone.
- TTNS satisfaction survey at 3-month follow-up. Can be conducted over the phone.
- Information will be tabulated on an Excel spreadsheet on my personal work desktop, password protected. Any paper data (bladder diary) will be de-identified and retained in a locked drawer in the locked office of the PI.
- General self-efficacy at baseline, week 6 and at the end of the trial. Can be conducted over the phone.
- CD-RISC at baseline, week 6 and at the end of the trial. Can be conducted over the phone.
- The medication and TTNS adherence survey at baseline then every 4 weeks. Can be conducted over the phone.
- The medication and TTNS % survey at baseline then every 4 weeks. Can be conducted over the phone.

1. Summary of Study Design

A randomized control trial of TTNS v sham-control in chronic SCI (n=60) performing intermittent catheterization on OAB medications will be performed to address the following Specific Aims:

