6. METHODS AND ASSESSMENTS

- a. Physical exam will be performed per usual care at TIRR, by the attending SCI physicians. Data will be retrieved from the electronic medical record and placed into the data spreadsheet. Missing data will be requested from the attending physician or directly from the patient.
- b. Transcutaneous Tibial Nerve Stimulation (TTNS) will be placed by trained research assistants in the clinic to determine if the subject meets I/E criteria. Skin inspection will be performed before and after the trial stimulation session at the electrode sites. Blood pressure will also be monitored during this trial for an additional safety measure to ensure autonomic dysreflexia is not occurring.
- c. The Bladder diary will be used to collect data use of TTNS with amperage and presence of toe flexion, pain score 0-10, as well as incontinence episodes and volumes. The research assistant (RA) will call weekly to capture the written data and monitor progress with the protocol.
- d. The RA will also perform the survey outcome measures (NBSS, I-QOL, CD-RISC, GSE, Medication adherence surveys and anticholinergic side effect questionnaire) at baseline every 4 weeks, 6 weeks and at 3-months. Surveys can be conducted over the telephone.

2. Randomization and Blinding

Subjects will be randomized to either TTNS or sham control (1:1) using a block size of 4 and stratified based on complete/incomplete SCI to ensure the equal allocation of the most severely injured in the two groups. The PI will be blinded to randomization and treatment allocation, managed by the research assistant.

3. Contraception and Pregnancy Testing

Females of childbearing age will have to adhere to medically recommended contraception if sexually active with men, such as condoms and/or birth control pills.

4. Study Visits and Procedures

- *Screening Visits and Procedures*

Screening will be performed in the SCI clinic by the PI or co-I SCI attendings.

Those that meet the I/E criteria will be approached for the study by the PI or co-I attendings. They have until the study period is complete to decide whether they want to participate. However, they will have to return to clinic to have the TTNS trial performed and the directions for home use.

- *Study Visits and Procedures*

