Subjects will have their first study visit after their normal clinic visit. Once consented, we will trial TTNS for a response of toe flexion. If they have a response, they will be included in the study. If no response or not tolerating electric stimulation, they will not be included in the study.

Participants will have direction in clinic on the use of the Stamobil+, including written, oral, and smartphone images/video if they have access.

The electric stimulation protocol will use stimulation frequency of 10 Hz and pulse width of 200ms in continuous mode for 30 minutes daily, beginning as soon as possible. The goal is 5 days per week of TTNS use for 3-months.

Subjects will be called weekly to capture the information of the TTNS log and to monitor progress of protocol. They will also be reminded to change electrodes weekly. 3 days prior to the NBSS call, the RA will contact the subjects to remind them to begin recording in their voiding diary for 2 days.

- *Final Study Visit:*

Upon completion of the 3-month study period, final voiding diary information will be collected and the post-trial questionnaires will be conducted.

- *Post Study Follow up and Procedures*

The data will be statistically analysed in the post-study follow up. Subject participation is not required.

- *Discontinuation Visit and Procedures*

If withdrawal occurs, no evaluation will be required for the final study visit, regardless of the withdrawal reason. There are no safety risks in withdrawing from this study at any point. OAB medications can be resumed at the prior efficacious dose.

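### Stopping the device is not separated from leaving the study, so week-12 data may go uncollected for people whose reason for stopping may be related to the outcome

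*Combined protocol and SAP*

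**What the plan says.** Section 3.5 (Withdrawal Criteria) introduces its list as "Possible reasons for discontinuation of study intervention". The three entries are incontinence that becomes intolerable once bladder medication is stopped, intolerance of the stimulation, and non-compliance. The last has no threshold, and the section does not say who decides.

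Section 6.4 (Discontinuation Visit and Procedures) says "If withdrawal occurs, no evaluation will be required for the final study visit, regardless of the withdrawal reason", and adds that "OAB medications can be resumed at the prior efficacious dose". Section 3.6 says "Subjects who drop out will be replaced by recruitment from the SCI clinic".

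Section 5 (Information gathered) sets the survey timing. For incontinence-related quality of life it reads: "I-QOL at baseline initial visit and then at 3-month follow-up. Can be conducted over phone". The side-effect survey has the same two time points, while NBSS is also repeated monthly in between. Both of these may likewise be done by telephone.

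Section 6 adds that "The research assistant (RA) will call weekly to capture the written data and monitor progress with the protocol".

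Section 11.2 plans group comparisons of change, mixed-effects models with number of sessions among the covariates, and a cited review of methods for non-random missing data. It names no analysis set and does not say how replaced participants are counted.

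**The concern.** Two of the three reasons for stopping are plausibly tied to outcome or arm. Intolerable incontinence during the wean is close to failing the primary endpoint and, if the device works, should be commoner under sham. Intolerance of stimulation is more plausible in the active arm, since section 5 puts active stimulation in the pilot at about 40 mA against 1 mA for sham. If such people leave before week 12 and are replaced, the final comparison can drift towards those who tolerated the wean and the device. The direction cannot be predicted.

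The primary endpoint has a further ambiguity. Someone who stops may return to the earlier dose. That person is a reducer on the last logged dose and a non-reducer on the dose taken afterwards, and no section says which counts.

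**Working it through.** **1. Whether the sections connect.** Section 3.5 speaks of discontinuing the intervention, section 6.4 of withdrawal and section 3.6 of dropping out. No sentence equates the three. The link is that the reasons for stopping the device sit under the heading Withdrawal Criteria, and nothing elsewhere says that a person off the device is still followed. The path from stopping, to no week-12 evaluation, to replacement is therefore open but not required.

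**2. What a stopper loses.** Take someone who stops and leaves after week 4, using the schedule of events in section 5.1:

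| Outcome | Post-baseline values planned | Lost |
|---|---|---|
| I-QOL | 1 (week 12) | 1 of 1 |
| Anticholinergic survey | 1 (week 12) | 1 of 1 |
| NBSS | 3 (weeks 4, 8, 12) | 2 of 3 |
| Voiding diary, if weekly | 12 | 8 of 12 |
| Voiding diary, if two days before each NBSS call (section 6.4) | 3 | 2 of 3 |

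**3. The plan's own figures.** Section 11.1 gives 21 per group for 83% vs 40%, 80% power, two-sided 0.05. The pooled normal formula is n = [1.96·√(2p̄(1−p̄)) + 0.842·√(p₁q₁+p₂q₂)]²/d². With p̄ = 0.615 and d = 0.43 it gives (1.349 + 0.520)²/0.185 = 18.9, so 19; 21 per group has 84.3% power. The 30 per arm is 21 × 1.4 = 29.4, rounded up. The allowance for loss is 60 − 42 = 18; section 5 expects 6.

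**4. How much of the primary endpoint could be undetermined.** Assume equal splits, each lost person replaced in the same arm, and replacements who complete.
- 6 losses: 3 per arm, 33 randomised, 3/33 = 9.1 points of that arm's rate.
- 18 losses: 9 per arm, 39 randomised, 9/39 = 23.1 points.

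Without replacement the same losses give 3/30 = 10 and 9/30 = 30 points. These are ranges of ignorance over all causes of loss, not estimates of bias. The share due to any section 3.5 reason is not given and could be 0.

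**5. Pilot experience.** All 16 completed (section 1.2). The one-sided 95% upper limit for non-completion solves (1−p)¹⁶ = 0.05, so p = 1 − 0.829 = 17%. The pilot was single-arm, without sham.

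**6. What full follow-up would do to power.** Let f be an assumed share who stop but are followed, with 30 per arm and nobody lost. Power is Φ[(d√n − 1.96·√(2p̄(1−p̄)))/√(p₁q₁+p₂q₂)]. In case A, a share f of the TTNS arm stops and then reduces at the control rate: p₁ = 0.83(1−f) + 0.40f, p₂ = 0.40. In case B, a share f of each arm stops, resumes the earlier dose and counts as not reduced: p₁ = 0.83(1−f), p₂ = 0.40(1−f).

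| f | A: rates | A: power | B: rates | B: power |
|---|---|---|---|---|
| 10% | 78.7% vs 40% | 88% | 74.7% vs 36.0% | 87% |
| 20% | 74.4% vs 40% | 78% | 66.4% vs 32.0% | 77% |
| 40% | 65.8% vs 40% | 52% | 49.8% vs 24.0% | 55% |

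With no stopping, power at 30 per arm is 94.8%.

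**The case against.** The best defence is that the plan already keeps most people in. Under section 5, someone who cannot tolerate a dose cut stays on the smallest dose they can manage and tries again the next week, so failing the wean normally leaves a recorded dose. Painful stimulation is turned down, and section 2.4 supplies hypoallergenic electrodes. Section 6.4 waives the final evaluation but does not forbid it, and its next sentence concerns the safety of withdrawing. Section 11.2 anticipates non-random missing data. All of this stands and lowers the likely number affected. None of it requires follow-up once the device has been stopped, and no missing-data method can supply an I-QOL value that was never collected.

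Three stronger readings are tempting, and the documents do not support them.

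- A reader might infer that low users of the device are to be removed. Non-compliance is undefined, and the stipend described beneath it in section 3.5 rewards completing diaries and logs, not sessions, so it may equally mean failing to report. The adherence surveys and the sessions covariate suggest that low users are meant to stay.
- A reader might infer a badly inflated false-positive rate. With a true 40% in both arms, if only TTNS non-reducers are removed and replaced, and only completers are analysed, the observed TTNS rate is 0.40/(1−f). At 30 per arm, f of 10%, 20% and 40% gives 44.4%, 50.0% and 66.7%, with rejection rates of about 6.4%, 12% and 55%. No section supports one-sided removal of that kind, so these are extremes.
- A reader might infer that non-compliance must be struck from the list. Once follow-up continues after stopping, that is unnecessary.

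**Conclusion.** The concern holds as a gap in the follow-up rules. The plan permits, without ordering, week-12 data to go uncollected for people whose reason for stopping may be related to the outcome, and it does not say that everyone randomised is analysed. The one inferred step is that a person taken off the device may be treated as withdrawn and as a drop-out. The heading of section 3.5 supports that reading and nothing contradicts it.

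The size of any bias cannot be derived from the documents and may be near zero. The 9.1 and 23.1 points show only how much would be left open under the plan's two loss figures, on the equal-split and replacement assumptions above. The plan should be changed because values not collected at week 12 cannot be recovered at analysis.

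**What to change.** 1. In section 6.4, replace the sentence waiving the final evaluation with: *Stopping the device for any reason is not withdrawal from the study; unless consent is withdrawn, weekly calls and the week-12 medication, NBSS, I-QOL and anticholinergic assessments continue, by phone if needed.* The week-12 urodynamic study may be optional for those who stop, since it needs a visit.
2. Add to section 3.6: *Any replacement is an additional randomised participant; everyone randomised is analysed in the assigned arm.* Under item 1, someone off the device but still followed is not a drop-out.
3. In section 11.2, state that the primary endpoint uses the medication dose actually taken at week 12, so a person who has resumed the earlier dose counts as not reduced.

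Non-compliance may remain as a reason to stop the device.

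The cost is amendment wording and at most 6 to 18 extra sets of week-12 phone assessments on the plan's own loss figures. People who cannot be reached or who withdraw consent will still be missing. The weekly calls are already scheduled for every participant. The statistical price is a possibly smaller observed effect: power at 30 per arm stays near 87% to 88% if 10% stop, and falls to about 77% to 78% if 20% do.

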4. TRIAL SCHEDULE

Table 3. Study Timeline

Task	Year 1				Year 2			
	1	2	3	4	1	2	3	4
Obtain IRB approval								
Register study with www.clinicaltrials.gov								
Subject screening and recruitment (n=60, ~2-6/month)								
Baseline assessments								
Neurogenic Bladder Symptom Score (NBSS) (SA 1.2)								
Incontinence quality of life (I-QOL) (SA 2.1)								
Anticholinergic Side Effects (SA 2.2)								
Collection of Voiding Diary Weekly								
Overactive Bladder Medication dosage (SA 1.1)								
Cath frequency, volumes, and incontinence (SA 1.2)								
Compliance								
Evaluate the efficacy of TTNS at home (SA 1)								
Evaluate the impact of TTNS on quality of life (SA 2)								
Analyze SA 1 & SA 2								
Present findings								
Development of manuscript(s)								

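### Withdrawals need no final evaluation and dropouts are replaced, yet the plan does not say whether withdrawn participants stay in the Aim 1.1 responder proportion or how they are classed

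*Combined protocol and SAP*

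**What the plan says.** All references are to the combined protocol and SAP.

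- **Section 3, Withdrawal Criteria.** Under the lead-in "Possible reasons for discontinuation of study intervention", the first item is "Intolerable incontinence after discontinuation of bladder medications". The section heading speaks of withdrawal and the lead-in of stopping the intervention, so it is unclear whether stopping the device also ends study participation.
- **Section 3, Subject Replacement.** "Subjects who drop out will be replaced by recruitment from the SCI clinic". Nothing says whether the replaced person's data are kept.
- **Section 6, Discontinuation Visit and Procedures.** "If withdrawal occurs, no evaluation will be required for the final study visit, regardless of the withdrawal reason". It adds that "OAB medications can be resumed at the prior efficacious dose".
- **Data collected before exit.** Section 6: "Subjects will be called weekly to capture the information of the TTNS log and to monitor progress of protocol". Section 3 pays participants for "logging bladder medication use and TTNS use/settings monthly", and the Section 4 timeline has a row for medication dosage under Aim 1.1.
- **Section 11.2.** It names a t-test or Wilcoxon test, mixed-effects models, and a cited method for non-random missing data. It names no analysis set and gives no rule for a withdrawn or replaced participant on the reduced/not-reduced outcome.
- **Expected dropout.** Section 5 anticipates 6 of 60. Section 11.1 allows for 40%.

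**The concern.** One listed reason for leaving is close to the definition of failure on Aim 1.1. Someone who leaves for that reason may go back to the earlier dose, and nobody is required to record what they take at week 12. With a replacement rule and no stated analysis set, the analyst must decide after the fact whether that person counts as reduced, counts as not reduced, or is left out in favour of a replacement.

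If failures leave the denominators, the responder rate rises in any arm that loses them. The between-arm difference then depends on how many failures each arm lost, which randomisation does not protect. A rule chosen once outcomes are visible cannot be shown to be independent of the result.

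**Working it through.** **Plan's own figure.** Inputs from Section 11.1: 40% vs 83%, two-sided 0.05, 80% power. The pooled two-proportion formula gives n = [1.96·√(2·0.615·0.385) + 0.842·√(0.24 + 0.1411)]² / 0.43² = 18.9, so 19 per group. The stated 21 is close to this and slightly generous. At the 30 per arm actually recruited, chi-square power by full binomial enumeration is 95% (Fisher exact 91%).

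**Set-up.** With 30 randomised per arm and L expected failures lost and left out, completer rate = 30p / (30 − L). At p = 0.40 an arm expects 12 responders and 18 failures. At p = 0.83 it expects 24.9 and 5.1. The total of six losses comes from Section 5. That all are failures, and how they split by arm, is assumed because the documents give neither. *Not replaced* means 60 randomised with completers varying binomially; *replaced* means recruitment continues to 30 completers per arm. Figures are chi-square, with Fisher in brackets where computed. A t-test or Wilcoxon test on the 0/1 indicator comes within about 1 point of chi-square.

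**No true effect (40% in both arms): type I error**

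| Failures lost | Completer rates | Not replaced | Replaced |
|---|---|---|---|
| 3 and 3 | 12/27 = 44.4% in both | 5% | 5% |
| 4.5 and 1.5 (3:1) | 12/25.5 = 47.1% vs 12/28.5 = 42.1% | 7% (4%) | 7% (4%) |
| 6 and 0 | 12/24 = 50% vs 12/30 = 40% | 12% (8%) | 12% (8%) |

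**Planned effect (sham 40%, TTNS 83%): power**

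| Failures lost (sham, TTNS) | Completer rates | Gap | Not replaced | Replaced |
|---|---|---|---|---|
| none | 40% vs 83% | 43 points | 95% (91%) | – |
| 6, 0 | 12/24 = 50% vs 83% | 33 points | 75% (70%) | 79% (71%) |
| 3, 3 | 12/27 = 44.4% vs 24.9/27 = 92.2% | 47.8 points | about 99% | about 99% |
| 40% of failures: 7.2, 2.04 | 12/22.8 = 52.6% vs 24.9/27.96 = 89.1% | 36.4 points | 85% (about 80%) | 90% (85%) |

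The last two rows differ in kind. Equal *numbers* lost per arm widen the gap, because TTNS has few failures to lose. An equal *share* of failures lost narrows it, because sham then loses more people.

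**Higher dropout.** Six of 60 is 10%, against 40% in Section 11.1. Keeping the 3:1 split but doubling the losses to twelve (9 and 3), with no true effect, gives 12/21 = 57.1% vs 12/27 = 44.4% and a simulated type I error of about 14%, not replaced.

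**All randomised analysed, these failures counted.** Type I error is 5% (3%) and power 95% (91%), whatever the split.

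**The case against.** The strongest reply has four parts.

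1. **The plan never says withdrawals are excluded.** This is correct. A reader might infer a completers-only analysis from the replacement rule and the waived evaluation, but no section states one. The text leaves the question open, and the point goes no further than that.
2. **Doses are recorded.** Weekly calls and paid monthly logs should put the dose on record up to exit, and the mixed models could use it. That stands, so it would be wrong to say withdrawn participants have no dose data. What is not required is the week-12 dose after exit, which may differ from the last recorded one if medication is resumed. The missing-data sentence in Section 11.2 points to a method but does not settle who is in the denominator of this proportion.
3. **Failing to wean is not an exit.** Under the medication reduction protocol in Section 5, someone who does not tolerate weaning stays on the lowest tolerable dose and continues. This limits the number of failures who leave. It does not remove the incontinence exit listed in Section 3.
4. **Withdrawal may be rare.** The home pilot (Section 1) reports 16 of 16 completing. It was small and single-arm, but it is direct evidence on retention at home and argues against the more extreme patterns. Against it, the plan's own sample size allows for 40% dropout.

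A blinded sham with identical usage instructions also makes strongly unequal withdrawal less likely when there is no true effect. Under a real effect, unequal numbers of failures are expected.

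**Conclusion.** The gap is real and should be fixed before analysis. The stated procedures leave the week-12 dose uncollected for participants likely to be Aim 1.1 failures, and the analysis section does not say how they or their replacements enter the proportion.

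The harm is conditional and, at six dropouts, modest: with no true effect, type I error runs from 5% to about 12% depending on the split. Under the planned effect the result can be understated or overstated. A reader might infer that the gap favours TTNS, or that equal losses are harmless. Neither is supported: losing sham failures costs power, and losing three failures in each arm inflates the difference by about 5 points.

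All of these figures assume that those lost are failures, that they are left out, and that they split between arms as shown. The documents support none of these as a forecast. The effect grows with dropout, and Sections 5 and 11.1 disagree on how much to expect.

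**What to change.** 1. Replace the Section 6 waiver with telephone collection of the week-12 OAB dose and NBSS from everyone who stops the device or withdraws, unless consent to contact is withdrawn.
2. In Section 11.2, make all randomised participants the primary Aim 1.1 analysis set, classed by the collected dose.
3. In Section 3, state that replacements are additional randomised subjects and that the people they replace stay in the analysis. State also whether the listed reasons end the intervention only or study participation too.
4. Pre-specify a fallback for a missing week-12 dose (for example, not reduced), with completer and alternative-imputation sensitivity analyses.
5. Reconcile the dropout figures in Sections 5 and 11.1.

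**Cost.** Protocol and SAP wording, and a few calls by staff who already call weekly. Reported rates fall where the fallback is used. If losses were unrelated to outcome and all were counted as not reduced, each rate is multiplied by (1 − loss). At 10% loss that is 36% vs 74.7%, with power of 88% at 30 per arm. At 40% loss it is 24% vs 49.8%, with power of 55%. Collecting the dose therefore comes first, and imputation is only the fallback.

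Two related matters need reconciling as separate points: the responder definition, which differs on whether continence or stable symptoms are also required (Sections 2, 5 and 11.1), and the passages on weaning and discontinuing medication (Sections 1, 3 and 5). Both affect how many failures leave and how they are classed.
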